5.7.3.3 Subgroup Analysis

No subgroup analyses are planned for the secondary endpoints.

5.7.3.4 Sensitivity Analysis

For castration maintenance (<20 ng/dL) rate during the study, the Kaplan-Meier estimate at Day 337 using the same strategies as Primary-S3 with castration maintenance criteria replacing with as <20 ng/dL will be provided.

5.7.4 Analysis of Other Secondary Efficacy Endpoints

No other secondary efficacy endpoint analyses are planned for this study.

5.7.5 Analysis of Exploratory Endpoints

No exploratory analyses are planned for this study.

5.8 Safety

5.8.1 General Consideration

All safety summaries and analyses will be based upon the Safety Set. All safety data will be included in subject data listings (see listing detail conventions in [Appendix 4](#)).

Associated Procedure / Instruction Reference	319480-SOP
Form Reference	080091-FOR v7.0

Baseline value definition is given in section [5.1.3](#).

5.8.2 *Extent of Exposure*

Administration of triptorelin embonate 22.5 mg 6-month formulation will be summarized by descriptive statistics for the following: duration of exposure, number of injections administered, number of subjects with at least one dose reduction or injection delayed. Duration of exposure will be defined in months as:

$([\text{last dose date} - \text{first dose date}] + 1) / (365.25/12)$.

- Exposure listing will also be generated.

5.8.3 *Adverse Event*

All adverse events (AEs) recorded in the eCRF will be coded using MedDRA dictionary. All AEs will be classified by MedDRA PT and SOC. Severity will be graded according to the National Cancer Institute - Common Terminology Criteria for Adverse Events (NCI-CTCAE) Version 5.0 or higher. Adverse events will be classified as TEAEs if meeting one of the rules below:

- Events with start date/time on or after the date/time of first IMP administration and within 168 days after the last dose of study treatment, or up to Day 337, whichever is later.
- Events whose severity worsens on or after the date/time of first IMP administration,

For AE with partial or missing start date, refer to [Appendix 2](#) for TEAE determination algorithm.

In the case where it is not possible to define an AE as treatment emergent or not, the AE will be classified by the most conservative case; i.e. treatment emergent.

The following summaries will be presented:

- Overview of TEAE,
- TEAE by SOC and PT,
- TEAE by PT,
- Most common ($\geq 10\%$) TEAEs by SOC and PT,
- TEAE by SOC, PT, and worst toxicity grade,
- Grade 3 or 4 TEAE by SOC and PT,
- TEAE by SOC, PT, and treatment relationship,
- Treatment-related TEAE by SOC, PT, and worst toxicity grade,
- Grade 3 or 4 treatment-related TEAE by SOC and PT,
- Non-serious TEAE by SOC and PT.

TEAE summaries will be presented in decreasing frequency of SOC, decreasing frequency of PT within SOC, and then in alphabetical order. TEAE summaries by PT will be presented in decreasing frequency of PT, and then alphabetically.

Multiple occurrence of TEAEs will be presented as follows:

- Participants will be counted at most once at the PT, and at most once at the SOC;

Associated Procedure / Instruction Reference	319480-SOP
Form Reference	080091-FOR v7.0

IPSEN GROUP

CONFIDENTIAL

D-FR-52014-245

SAP Final: Version 1.0: 30 January 2023

PAGE 22/43

- Participants reporting multiple TEAEs coded within the same SOC/ PT will be presented in the worst-case grade category (grade order: 5>4>3>2>1>missing) ever reported in that SOC/PT;
- Participants reporting multiple TEAEs coded within the same SOC/ PT will be presented in the TEAE with the worst-case relationship to study treatment (order: related > not related > missing) ever reported;
- For TEAE summary by worst toxicity grade, participants reported single occurrence TEAE while the associated toxicity grade is missing, the participant will be presented in the toxicity grade missing category;
- TEAEs with missing relationship to study treatment will be considered treatment-related in the summary.

The number of events will also be displayed in the summary tables, when applicable.

Deaths, SAEs, and Other Significant Adverse Events

The following summaries will be presented:

- Serious TEAE by SOC and PT,
- Most common ($\geq 5\%$) serious TEAEs by SOC and PT,
- Treatment-related serious TEAE by SOC and PT,
- TEAEs leading to treatment discontinuation by SOC and PT,
- TEAE leading to treatment interruption by SOC and PT,
- TEAEs leading to a dose reduction by SOC and PT,
- Death summary.

By-subject listing will be produced for all AEs, all serious adverse events (SAEs), all AEs leading to dose reduction, treatment interruption, treatment discontinuation, and fatal AE. Treatment emergence status will be flagged in the listing whenever applicable.

5.8.4 *Laboratory Data*

Clinical safety laboratory tests will be assessed by local laboratories. All laboratory data will be presented in the units of International System of Units (SI).

Haematological and biochemical toxicities will be graded according to the NCI-CTCAE criteria, where available. The toxicity grades will be assigned programmatically by applying the NCI-CTCAE guideline as described in Section 7 (11). All scheduled and unscheduled laboratory test results will be included in the worst toxicity grade summary. For white blood cells, neutrophils, platelets and haemoglobin, with associated grade 3 or 4 toxicities, nadir and day to nadir from most recent injection will be presented in the listing.

The neutrophils values will be imputed as defined in Section 7 (12).

The following summaries will be provided:

Associated Procedure / Instruction Reference	319480-SOP
Form Reference	080091-FOR v7.0

- A summary of the actual and change from baseline in each laboratory haematology parameter (platelet count, haemoglobin, white blood cell counts, neutrophils, lymphocytes, monocytes, eosinophils, basophils) and in each laboratory biochemistry parameter (creatinine, non-fasting glucose, aspartate aminotransferase, alanine aminotransferase, alkaline phosphatase, total bilirubin and conjugated bilirubin) at Day 337,
- Shift from baseline to end of study based on abnormalities,
- Shift from baseline to end of study based on CTCAE toxicity grading.

The following listings are to be provided:

- A listing of all laboratory data (with flag indicating abnormal values),
- A listing of laboratory data for subjects with at least one post-baseline abnormal value (with flag indicating abnormal values),
- A listing of relevant laboratory data for subjects with at least one CTCAE grade 3 or higher post-baseline laboratory result.

5.8.5 *Vital Signs*

The following summaries will be presented:

- Summary of the actual and change from baseline in each vital sign parameter (systolic blood pressure, diastolic blood pressure, heart rate, respiratory rate, temperature) by timepoint,
- Summary of subjects experiencing Potentially Clinically Significant Abnormalities (PCSA). Note: PCSA criteria are defined in [Appendix 1](#) for systolic blood pressure, diastolic blood pressure and heart rate.
- Shift from baseline to each post-baseline visit based on clinical abnormality evaluation.

The following listings are to be provided:

- All vital sign data, with abnormal value flagged.
- Listing of PCSA. All relevant vital sign data for subjects with at least one post-baseline PCSA record.

5.8.6 *Electrocardiogram*

The following quantitative electrocardiogram (ECG) measurements will be taken during the study:

- RR interval (msec),
- PR interval (msec),
- QRS duration (msec),
- QT interval (msec),
- Fridericia corrected QT (QTcF) interval (msec).

An overall investigator assessment of ECG will be provided as “normal”, “abnormal, not clinically significant” and “abnormal, clinically significant”.

Associated Procedure / Instruction Reference	319480-SOP
Form Reference	080091-FOR v7.0

The following summaries of ECG data will be provided:

- Summary of the actual and change from baseline in each ECG parameter by timepoint (Baseline and Day 337),
- Summary of subjects experiencing PCSA. Note: PCSA criteria are defined in [Appendix 1](#) for QTc and delta QTc.
- Shift from baseline based on clinical abnormality evaluation.

A listing of ECG data is to be provided with abnormal value and PCSA records flagged.

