- See Appendix [10.2](#) for the list of clinical laboratory tests to be performed and to the SoA ([Section 1.3](#)) for the timing and frequency. Assessments will be analysed by the local laboratory.

- The investigator must review the laboratory report, document this review, and record any clinically significant changes occurring during the study as an AE. The laboratory reports must be filed with the source documents.
- Abnormal laboratory findings associated with the underlying disease, are not considered clinically significant unless judged by the investigator to be more severe than expected for the participant's condition.
- All laboratory tests with values considered clinically significantly abnormal during participation in the study or within 168 days after the last dose of study intervention should be repeated until the values return to normal or baseline or are no longer considered clinically significant by the investigator or medical monitor.
 - If clinically significant values do not return to normal/baseline within a period of time judged reasonable by the investigator, the aetiology should be identified, and the sponsor notified.
 - All protocol-required laboratory tests, as defined in Appendix 10.2, must be conducted in accordance with each local laboratory practice and the SoA (Section 1.3).
 - If laboratory values from non-protocol specified laboratory tests performed at the study site laboratory require a change in participant management or are considered clinically significant by the investigator (e.g. SAE or AE or dose modification), then the results must be recorded in the eCRF.

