8.4.1 Time Period and Frequency for Collecting AE and SAE Information

All AEs and SAEs will be collected from the signing of the ICF until EoS at the time points specified in the SoA (Section 1.3).

Medical occurrences that begin before the start of study intervention but after obtaining informed consent will be recorded on the AE section of the case report form.

All SAEs will be recorded and reported to the sponsor or designee immediately and under no circumstance should this exceed 24 hours of awareness of the event, as indicated in

Appendix 10.3. The investigator will submit any updated SAE data to the sponsor within 24 hours of it being available.

Investigators are not obligated to actively seek information on AEs or SAEs after conclusion of the study participation. However, if the investigator learns of any SAE, including a death, at any time after a participant has been discharged from the study, and he/she considers the event to be reasonably related to the study intervention or study participation, the investigator must promptly notify the sponsor.

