5.1.1 Outputs Presentation

5.1.1.1 Presentation of Visits / Timepoints

For by-visit summaries, the nominal visit as collected in the Electronic Case Report Form (eCRF) will be used in general for analysis purpose unless stated otherwise. Analysis visit window described in Section 6.1 will be used for slotting actual testosterone and prostate-specific antigen (PSA) assessment dates into planned schedule. Unscheduled visits will not be displayed in summaries but will be listed.

Visits in the TFLs will be presented as follows and in the following order:

Period	Long Visit Name	Short Name	Protocol Time Interval
Screening	Day -28 to Day – 1 (Screening)	Scr	
Intervention Period	Day 1 (Baseline)	Bsl	
	Week 1 – Day 3	D3	Day 3 after first injection
	Week 1 – Day 7	D7	Day 7 after first injection
	Week 4 – Day 29	D29	±3 day
	Week 12 – Day 85	D85	±3 day
	Week 20 – Day 141	D141	±3 day
	Week 24 – Day 169	D169	±3 day
	Week 25 – Day 171	D171	Day 3 after last injection
	Week 25 – Day 175	D175	Day 7 after last injection
	Week 36 – Day 253	D253	±3 day
EoS/ED	Week 44 – Day 309	D309	±3 day
	Week 48 – Day 337	D337	±3 day

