5.1.2 Descriptive Statistics

Due to the single-arm nature of the study, all statistical analyses will be descriptive. All raw and derived variables will be listed and described using summary statistics. For categorical variables, summary statistics will be displayed using descriptive statistics by frequency count and percentages by category. The missing category will be presented if applicable. Unless otherwise specified, participants with missing data will be included in the calculation of percentages. For quantitative variables, summary statistics will be displayed using descriptive statistics by number of observations, mean, standard deviation (SD), first quartile, median, third quartile, minimum and maximum. Frequency and proportion of missing data will be displayed.

Associated Procedure / Instruction Reference	319480-SOP
Form Reference	080091-FOR v7.0

For the efficacy analyses, the descriptive statistics of treatment effects and corresponding 95% CIs for the primary endpoint and secondary endpoints will be presented if applicable.

5.1.3 *Baseline Value*

Unless otherwise specified, baseline is defined as the last non-missing measurement taken prior to first Investigational Medicinal Product (IMP) administration (including unscheduled assessments).

5.1.4 *Reference Start Date and Study Day*

Reference start date is defined as the day of the first IMP administration.

The day of the first IMP administration will be Day 1. Study day will be calculated as:

- The difference between the event date and the reference date plus one day, if the event is on or after the reference date.
- The difference between the event date and the reference date, if the date of event is prior to the reference date.

Study day will appear in any listings where an assessment date or event date appears.

In case of partial or missing event date, study day will appear missing while any associated durations will be presented based on the imputations described in [Appendix 2](#).

5.2 **Enrolment, Disposition and Analysis Sets**

A Listing presenting study treatment dispensation details will be provided (Listing 16.1.7).

Following disposition summaries will be provided:

- Summary table with the number and percentage of participants screened, screen failed, reason for screen failures, enrolled, treated, having completed the study, withdrawn and reason for withdrawal,
- Summary table with the number and percentage of participants enrolled per visit,

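### Read literally, the SAP's TEAE window can close up to 3 days before a permitted final visit, so new AEs starting in that gap miss the TEAE tables

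*SAP*

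**What the plan says.** - **TEAE rule.** SAP 5.8.3 has two routes. A new event qualifies if its start date/time is on or after first dosing and "within 168 days after the last dose of study treatment, or up to Day 337, whichever is later". The other route is "Events whose severity worsens on or after the date/time of first IMP administration", which has no end date.
- **Study day.** SAP 5.1.4 sets "The day of the first IMP administration will be Day 1" and counts later days as "The difference between the event date and the reference date plus one day, if the event is on or after the reference date".
- **Visit windows.** SAP 5.1.1.1 lists the second injection as "Week 24 – Day 169 D169 ±3 day" and the final visit as "Week 48 – Day 337 D337 ±3 day". The Schedule of Activities in Protocol 1.3 gives the same windows.
- **AE collection.** Protocol 8.4.1: "All AEs and SAEs will be collected from the signing of the ICF until EoS at the time points specified in the SoA".
- **Tests at the final visit.** Protocol Table 5 places safety laboratory tests at screening and EoS/ED only. Protocol Table 1 does the same for the ECG, apart from clinically indicated recordings. Under Protocol 8.3.5 the investigator must "record any clinically significant changes occurring during the study as an AE". Protocol 8.3.3 has the equivalent rule for the ECG.
- **Outputs.** Every AE incidence table named in SAP 5.8.3 is a TEAE table; only the death summary is not labelled that way. By-subject listings cover all AEs and SAEs, with emergence status flagged.
- **Endpoint.** Both documents define the safety endpoint as TEAE incidence over the whole study, and gloss that as ending at Day 337.

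**The concern.** AE collection ends at a visit, while AE counting ends on a calculated date. The date can come first even when the visit is on schedule. Whether a new event starting in those last days is counted then depends on which permitted day the participant attended and on when he had his second injection.

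The final visit is where this is most likely to matter, because it is the only scheduled occasion after dosing for safety laboratory tests and the ECG. A new clinically significant finding there has to be recorded as an AE. If its onset is entered as the sample or recording date, it can fall beyond the limit. The protocol synopsis promises tabulation of all AEs as well as TEAEs, but the SAP names no all-AE table that would catch such an event.

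What is at stake is a possible undercount, in one direction only, in a stated secondary safety endpoint. The primary endpoint, the sample size and the success criterion are not affected.

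**Working it through.** **Inputs.** Second injection D2 = Day 169 ±3, so Day 166 to 172. Final visit V = Day 337 ±3, so Day 334 to 340. Cut-off C for the start-date route = max(337, D2 + 168).

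**The plan's own figure.** 169 + 168 = 337. This reproduces the nominal final day in SAP 6.1, where Day 337 equals D2 + 168. With the second dose exactly on Day 169, both limits in the rule therefore coincide at Day 337.

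**Enumeration.** A visit day is exposed when V > C. The protocol does not say whether ±3 runs from Day 1 or from the second injection, so both are shown.

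| D2 | Cut-off C | Exposed visit days, window from Day 1 | Exposed visit days, window from D2 + 168 |
|---|---|---|---|
| 166 | 337 | 338, 339, 340 | none |
| 167 | 337 | 338, 339, 340 | 338 |
| 168 | 337 | 338, 339, 340 | 338, 339 |
| 169 | 337 | 338, 339, 340 | 338, 339, 340 |
| 170 | 338 | 339, 340 | 339, 340, 341 |
| 171 | 339 | 340 | 340, 341, 342 |
| 172 | 340 | none | 341, 342, 343 |

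Window from Day 1: 3 + 3 + 3 + 3 + 2 + 1 + 0 = 15 of 7 × 7 = 49 pairs. Window from D2 + 168: 0 + 1 + 2 + 3 + 3 + 3 + 3 = 15 of 49. On either reading the gap is at most 3 days. A participant who has no second dose but stays in follow-up has a cut-off of max(337, 1 + 168) = Day 337, so he can be exposed too.

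**From pairs to participants (illustrative).** 15/49 = 0.306. If dosing and visit days were independent and evenly spread over their windows, which the documents do not state, about 0.306 × 130 = 40 of the planned 130 evaluable participants would attend after the cut-off. These are participants exposed to the gap, not lost events.

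**From participants to events (illustrative).** Suppose 1% to 5% of those 40 had a new significant finding dated to that visit; this range is assumed. The loss would be 40 × 0.01 = 0.4 to 40 × 0.05 = 2 participants.

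**After the change.** With C = max(337, D2 + 168, V), V can never exceed C, so the uncovered visit days fall from at most 3 to 0.

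**The case against.** The strongest reply is that Day 337 is the name of the final visit. Both documents say that a participant completes at the Day 337 visit, summarise laboratory change at Day 337 despite the ±3 days, and equate Day 337 with the whole study in the endpoint. The SAP's testosterone window for that visit is open-ended from D2 + 155. On this reading there is no gap, and choosing the later of two limits suggests an inclusive intent. This is a possible reading, and it may be what was meant. But the clause tests a start date/time and sets Day 337 beside a 168-day count, and the SAP defines study day by arithmetic. A programmer would most naturally code a numeric limit. The text needs to settle the question.

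A reader might also infer that AEs found at a late final visit vanish from all AE summaries. The documents do not support that:

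- Status depends on onset, not discovery, so an event reported on Day 340 that began by the cut-off is still counted.
- Worsening events qualify with no end date.
- Events whose status cannot be determined default to treatment-emergent.
- Listings of all AEs and SAEs, and the death summary, are unaffected.
- Final-visit laboratory and ECG values enter their change and shift summaries, the laboratory toxicity-grade summaries and the ECG summary of potentially clinically significant abnormalities, whatever the TEAE status.

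Nor is the final visit the only occasion on which such findings can arise, since unscheduled tests and ECGs are allowed; it is the only scheduled one after dosing.

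Finally, it would be unfair to say that the SAP narrows the protocol. Protocol 9.4.3 limits TEAEs to the treatment period without a day count, but the protocol endpoint itself stops at Day 337, and the SAP extends that where last dose + 168 days is later.

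**Conclusion.** The point stands as a minor specification gap. Read literally, the start-date rule can close 1 to 3 days before a protocol-compliant final visit, in 15 of 49 permitted day pairs. A new AE with onset in that gap is collected and listed but enters no TEAE incidence table. The effect can only lower reported incidence.

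Two assumptions carry the practical consequence: that Day 337 is coded as a study day, and that a finding's onset is dated to the sample or visit. Neither document gives an onset-dating rule for laboratory or ECG findings.

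A reader might take 15 of 49 as meaning that about 31% of final-visit AEs, or the AEs of about 40 participants, are lost. It does not mean that. It counts combinations of days, it becomes a share of participants only under even and independent timing, and it says nothing about how many of them have a new event in those days. The number of events lost is probably small.

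**What to change.** In SAP 5.8.3, end the start-date window at the latest of three dates: last dose + 168 days, Day 337, and the participant's EoS/ED visit date. Because this adds a third term to a rule that already takes the later date, no event now counted would be removed. In the endpoint text of both documents, replace the Day 337 limit with: up to the Day 337 (EoS/ED) visit. If Day 337 was always meant as the visit, the edit simply states that.

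The cost is one line in the SAP, matching endpoint wording and one derivation in the programming. No new data are needed, and a few more events may be counted. It should be settled before database lock. Adding the all-AE tables promised in the protocol synopsis would also make such events visible, but would leave the TEAE endpoint itself unchanged.

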5.8.7 Physical Examination

The following summaries will be provided:

- Summary of subjects reporting abnormal finding in physical examination by body system (cardiovascular system, respiratory system, gastrointestinal system, neurological system, and other) for a shift from baseline (normal versus abnormal) to each post-baseline visit,
- Summary of the actual and change from baseline in weight and BMI by timepoint,
- Summary of subjects meeting PCSA criteria in weight (defined in [Appendix 1](#)).

By-subject physical examination listing will be provided with records meeting PCSA criteria or being considered as clinical abnormal flagged.

Associated Procedure / Instruction Reference	319480-SOP
Form Reference	080091-FOR v7.0

IPSEN GROUP

CONFIDENTIAL

D-FR-52014-245

SAP Final: Version 1.0: 30 January 2023

PAGE 25/43

6 DATA HANDLING

6.1 Visit window

The time window for visit/timepoints will be applied as below for the blood samples for testosterone. In case of multiple unscheduled and planned visits enclosing within the defined analysis time interval, the non-missing value in a visit closest to the target visit day will be used in the summary tables.

Study phase	Scheduled visit	Protocol Time Interval	Analysis Time Interval* (days)
Screening	Day -28 to Day -1		-28 to -1
Intervention Period			
	Day 1 (first injection)	<1	<=1
	Week 1 – Day 3	3	2 to 5
	Week 1 – Day 7	7	6 to 18
	Week 4 – Day 29	29	19 to 57
	Week 12 – Day 85	85	58 to 113
	Week 20 – Day 141	141	114 to 155
	Week 24 – Day 169 (second injection)	169 (D2)	156 to D2
	Week 25 – Day 171	171 (D2+2)	D2+1 to D2+4
	Week 25 – Day 175	175 (D2+6)	D2+5 to D2+45
	Week 36 – Day 253	253 (D2+84)	D2+46 to D2+112
	Week 44 – Day 309	309 (D2+140)	D2+113 to D2+154
End of Study/Early Discontinuation	Week 48 – Day 337	337 (D2+168)	≥D2+155

*Analysis visit window after screening are defined using the mid-point between each scheduled visit and reset with the second injection.

6.2 Unscheduled Visits, Retest, Withdrawal Visit,

All listings will include retest measurement and assessments from unscheduled visits. For by-visit summary, only planned visits in the protocol will be presented.

Assessments from unscheduled visit and retest measurements will be included for baseline value determination whenever applicable. These measurements will also be used to determine worst toxicity grade for laboratory data, or meeting PCSA criteria in vital signs or ECG.

If an assessment requires a retest (for example, safety laboratory, vital signs and ECG), the closest non-missing value to the scheduled visit will be used in the summary tables.

Participants who have withdrawn early from the study have their last assessment entered at the end of study / early discontinuation visit in the eCRF.

Associated Procedure / Instruction Reference	319480-SOP
Form Reference	080091-FOR v7.0

IPSEN GROUP

CONFIDENTIAL

D-FR-52014-245

SAP Final: Version 1.0: 30 January 2023

PAGE 26/43

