7.2 Participant Discontinuation/Withdrawal from the Study

- A participant may withdraw from the study at any time at his own request or may be withdrawn at any time at the discretion of the investigator for safety, behavioural or compliance reasons.
- At the time of discontinuing from the study, if possible, an early discontinuation visit should be conducted, as shown in the SoA. See SoA for data to be collected at the time of study discontinuation and for any further evaluations that need to be completed.
- The reason for discontinuation will be recorded in the eCRF.
- If the participant withdraws consent for disclosure of future information, the sponsor may retain and continue to use any data collected before such withdrawal of consent.
- If the participant requests to discontinue the study intervention, they will be asked to be followed for the study procedures.
- If the participant withdraws consent for any further contact, the investigator will explain in the medical records as to whether the withdrawal is only from further receipt of study intervention or also from study procedures. This information must be entered in the eCRF.
- If a participant withdraws from the study, he may request destruction of any samples taken and not tested, and the investigator must document this in the site study records.
- A participant will be withdrawn from the study if they have inadequate testosterone suppression (defined as >50 ng/dL detected at least 30 days after the first administration of study intervention and on two consecutive measurements at least 2 weeks apart, at either a scheduled or unscheduled study visit).

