
 To demonstrate the effect of triptorelin embonate 22.5 mg 6-month formulation administered subcutaneously to suppress the 'acute-on-chronic' effect following the administration of the second dose 	
 Percentage of participants castrated on Day 3 and Day 7 after each injection administered on Day 1 and Day 169 (castration defined as testosterone <1.735 nmol/L (50 ng/dL))

 To demonstrate the effect of triptorelin embonate 22.5 mg 6-month formulation administered subcutaneously in the maintenance of PSA 	
 Percent change in PSA from baseline (prior to injection) at Day 169 and Day 337 (Percent change in PSA defined as the absolute value of difference between the PSA values at Day 169 and Day 337 and the baseline value divided by the baseline value)

Associated Procedure / Instruction Reference	319480-SOP
Form Reference	080091-FOR v7.0

Objectives	Endpoints

 To demonstrate the safety profile of triptorelin embonate 22.5mg 6-month formulation administered subcutaneously 	
 Incidence of TEAEs (including local tolerability) throughout the study i.e. up to Day 337 Change from baseline in clinical safety laboratory parameters (blood chemistry and haematology) at Day 337 Change from baseline in physical examination at Day 169 and Day 337 Change from baseline in ECG at Day 337 Change from baseline in vital signs (blood pressure and heart rate) at each visit up to Day 337

AE=adverse event; ECG=electrocardiogram; PSA=prostate-specific antigen; TEAE=treatment-emergent adverse event

Note: A list of laboratory parameters to be assessed during the study are presented in Protocol Appendix 10.2.

- Hypotheses**

Hypotheses for this study are defined below.

The primary objective of this study is to evaluate the efficacy triptorelin embonate 22.5 mg (6-month formulation) administered subcutaneously in maintaining serum testosterone castrate levels during the study (maintenance of castration defined as testosterone <1.735 nmol/L (50 ng/dL) at Day 29, Day 85, Day 141, Day 169, Day 253, Day 309 and Day 337) with two complete study intervention administrations. Thus, the null hypothesis to be tested is as follows:

Null hypothesis: percentage of participants castrated (serum level of testosterone <1.735 nmol/L) from date of first dose to Day 337 is less than or equal to 90%.

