2.3 Sample Size Determination and Power

This single-arm study is designed to demonstrate that the percentage of participants remaining castrated (maintenance of castration defined as testosterone <1.735 nmol/L (50 ng/dL) at Day 29, Day 85, Day 141, Day 169, Day 253, Day 309 and Day 337) during the study is greater than 90%. Considering an observed castration maintenance in 97% of participants, 130 eligible participants are required to demonstrate the efficacy of the triptorelin 6-month formulation with approximately 90% power and a one-sided alpha of 0.025 using an exact binomial test. The objective will be achieved if the lower bound of the 95% confidence interval (CI) of the observed rate is greater than 90%.

Considering a drop-out rate of 10%, 145 participants will be included in the study.

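### The closest-to-target rule can let a nearer retest replace a planned testosterone value of 50 ng/dL or more, and the SAP does not say how the primary responder flag treats that value

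*SAP*

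**What the plan says.** The primary endpoint (Protocol 3, SAP 2.1 and 5.7.2.1) is testosterone below 50 ng/dL at seven named visits: Days 29, 85, 141, 169, 253, 309 and 337. The protocol allows ±3 days around each.

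SAP 5.1.1.1 says that the Section 6.1 windows "will be used for slotting actual testosterone and prostate-specific antigen (PSA) assessment dates into planned schedule". Those windows are wide: Days 19 to 57 for Day 29, and Days 58 to 113 for Day 85. If planned and unscheduled visits fall in the same window, "the non-missing value in a visit closest to the target visit day will be used in the summary tables". There is no worst-value rule for testosterone and no tie-break. SAP 6.2 uses unscheduled values for worst-case safety findings only.

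Unscheduled testosterone samples are foreseen. Protocol 7.2 bases withdrawal for inadequate suppression on values above 50 ng/dL "on two consecutive measurements at least 2 weeks apart, at either a scheduled or unscheduled study visit".

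The FAS note (Protocol 9.3, SAP 4) keeps a man with incomplete data in the FAS if he has a value of 50 or more. Intercurrent events 1 to 3 in SAP 5.7.2.1 exclude men with incomplete data only when no such value exists. Neither place says how the retained man is scored.

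The SAP null hypothesis is that the castration rate "from date of first dose to Day 337 is less than or equal to 90" percent, which describes a continuous period rather than seven visits.

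**The concern.** The trial claims that castration is maintained. If the value used at a visit is chosen only by its distance from the target day, an observed loss of castration at a planned visit can disappear from the primary rate because a later sample happened to lie nearer the target. Retests seem more likely after a high value than after a low one. That is reasoning, not something the documents report, but if it holds, the replacements would tend to favour the drug.

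The second problem is a missing scoring rule. A value of 50 or more can be the sole reason a man with a missed visit is in the FAS. If that value is unscheduled and another sample in the window is nearer the target, Section 6.1 discards it. He then has no selected value of 50 or more and an incomplete set of visits, and the SAP does not say whether he is a responder.

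**Working it through.** **Does the rule reach the primary analysis?** SAP 5.7.2.2 is silent and the Section 6.1 sentence mentions only summary tables. Three places point to yes:
- SAP 5.1.1.1 slots testosterone by these windows.
- In SAP 5.7.2.3, sensitivity analysis S1 applies the window and S2 removes it.
- Protocol 3 lists analyses without the visit window among the secondary estimands.

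This is an inference, and it is the only reading that fits all three.

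**Retest route.** A later retest replaces the planned draw when |retest day − target| < |draw day − target|. For target Day 85:

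| Planned draw (≥50) | Distance | Retest days (<50) that replace it |
|---|---|---|
| Day 82 | 3 | Days 83 to 87 |
| Day 83 | 2 | Days 84 to 86 |
| Day 84 | 1 | Day 85 |
| Day 85 to 88 | 0 to 3 | none |

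An on-schedule draw is therefore exposed only if it is 1 to 3 days early and retested within 5 days. Draws on Days 82 and 88 tie at distance 3, and the SAP does not resolve ties. At Day 169 the window closes on the day of the second injection, so a pre-dose sample taken that day cannot be replaced by a later one.

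The confirmatory draw in Protocol 7.2 cannot cause replacement of an on-schedule draw. It comes at least 14 days later, so after a Day 82 draw it falls on Day 96 or later, 11 or more days from target.

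**Dropped unscheduled value.** If Day 85 is below 50 and an unscheduled Day 100 value is 50 or more, the distances are 0 and 15, and the Day 100 value is not used. Values on Days 2 to 18 (17 days) and from 1 to 45 days after the second injection (45 days) go to visits outside the primary endpoint. If the second injection is on Day 169, that is (17 + 45)/336 = 18% of post-dose days.

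**Reproducing the design.** The inputs, all from SAP 2.3, are "Considering an observed castration maintenance in 97% of participants", a null rate of 90%, "130 eligible participants are required", and "approximately 90% power and a one-sided alpha of 0.025 using an exact binomial test". The smallest r with P(X ≥ r | 130, 0.90) ≤ 0.025 is 124, so at most 6 failures are allowed. Exact alpha is P(X ≥ 124 | 130, 0.90) = 0.0207, and power is P(X ≥ 124 | 130, 0.97) = 0.903. With 10% dropout, 130/0.90 = 144.4, rounded up to 145. The stated figures reproduce.

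**Boundary.** Clopper-Pearson lower 95% bounds:
- 124/130 (95.4%): 90.2%, success
- 123/130 (94.6%): 89.2%, failure

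**Effect of masking.** Let f be the share of true failures scored as maintained. The documents give no value for f, so the values below are assumptions. The apparent rate at a true 90% is 0.90 + 0.10f, and the chance of success is P(X ≥ 124 | 130, 0.90 + 0.10f):

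| f | Apparent rate | Chance of success |
|---|---|---|
| 0 | 90.0% | 2.1% |
| 5% | 90.5% | 3.1% |
| 10% | 91.0% | 4.6% |
| 20% | 92.0% | 9.7% |

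**The case against.** The strongest reply is that the rule is pre-specified and blind to the value. A nearer value of 50 or more replaces a farther value below 50 just as readily. Testosterone is measured centrally with no stated turnaround, so nothing shows that a result-driven retest within 5 days would happen. Protocol 8 allows repeats for technical problems, where replacement is proper. Sustained loss of castration leads to withdrawal, so exposure is mainly to isolated values. S2 and S3 do not use the window, and the listings show retests and unscheduled values. All of this stands. It limits the likely size, but it does not supply the missing rule, and sensitivity analyses in another set do not correct the primary rate. A one-man reversal at the boundary is also a feature of any exact test; it shows that single classifications matter, not that this rule is unusually harmful.

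Two stronger readings are tempting. A reader might infer that every unscheduled value of 50 or more left out is a real failure scored as success. On the seven-visit endpoint it is not an endpoint measurement; on the hypothesis wording it is. SAP 8 says the hypothesis was reworded to follow the protocol endpoints, so the documents do not settle this in favour of an any-time endpoint. A reader might also infer that the FAS note and intercurrent events 1 to 3 contradict Section 6.1. They decide who is analysed, not how he is scored, so this is a gap rather than a contradiction.

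**Conclusion.** The point holds in limited form. If the Section 6.1 windows feed the primary responder flag, as the rest of the plan implies, a planned value of 50 ng/dL or more can be replaced by a retest below 50, and nothing in either document prevents it. A man retained in the FAS because of such a value has no stated score. The retest route needs an early draw and a prompt retest, and its frequency is unknown. The consequence could still be decisive at 123 versus 124 of 130. Under assumed masking of 5% to 20% of failures, the one-sided error at a true 90% would be 3.1% to 9.7%, against 2.1% by design and a nominal 2.5%. Those percentages illustrate sensitivity; they do not estimate what this trial would see. The matter is worth settling before database lock because it concerns the primary endpoint and is cheap to settle.

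**What to change.** Keep the closest-value rule for by-visit summaries, and add a tie-break. In SAP 5.7.2.2, state for the primary responder flag:

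- (a) A planned-visit value of 50 ng/dL or more at any of the seven endpoint visits is a failure. It cannot be replaced by a retest or unscheduled value unless a technical error with the sample is documented.
- (b) A participant kept in the FAS because of a value of 50 ng/dL or more is a non-responder.

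Add a pre-specified sensitivity analysis that counts any valid value of 50 or more, scheduled or unscheduled, through Day 337 as failure. This addresses the difference between the seven-visit endpoint and the hypothesis wording, and covers values slotted to visits outside the endpoint. It belongs in a sensitivity analysis because failure would then depend partly on how often a man is sampled, whereas the endpoint is defined at seven visits.

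The cost is a few sentences in the SAP, one derivation and one extra table. The sample size is unchanged. The downside is that the reported rate may be slightly less favourable. Under (b), an unscheduled value of 50 or more counts in the primary analysis for a man with a missed visit but only in the sensitivity analysis for a man with complete visits; the SAP should say so openly.
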